[Subjects who transferred from studies RAJ3 or RAJ4] Chest radiography is taken at the Week 0 visit, or data obtained within 28 days prior to the Week 0 visit may be used.  
If a respiratory AE is observed, a chest radiography may be taken at any time as necessary, even in an unscheduled visit.
- m. Blood samples for pharmacodynamics (lymphocyte subset assay) are collected before the first dose of the study drug on the day of the Week 0 visit.
- n. Assessment of disease activity: **Physician** – TJC (68 joints), SJC (66 joints), PGA (VAS); **Subject** – SGA (VAS), subject's assessment of pain (VAS), HAQ-DI, WPAI, and SF-36V2®.
- o. SF-36v2® is administered every 4 weeks until Week 48 and every 24 weeks after Week 48 to subjects from study RAJ1 and every 24 weeks throughout the study period to subjects from studies RAJ3 or RAJ4.
- p. WPAI is administered only to subjects who transferred from studies RAJ3 or RAJ4.
- q. AEs must be collected from the time of the administration of the first dose of study drug to the end of all assessments at the end of study (at time of follow-up).

- CONFIDENTIAL -

- r. After all of the assessments and tests scheduled for Week 0 have been completed, the subjects will receive the first dose of the study drug at each study center.
- s. [Subjects who transferred from study RAJ1] If the study is terminated before the Week 48 visit, the specified date for the study visit at the end of treatment will be the date of the previous visit + 28 days (allowable range,  $\pm 7$  days). If the study is terminated in or after the Week 48 visit, the specified date for the study visit at the end of treatment will be the date of the previous visit + 84 days (allowable range,  $\pm 14$  days).  
[Subjects who transferred from studies RAJ3 or RAJ4] The specified date for the study visit at the end of treatment will be the date of previous study visit + 84 days (allowable range,  $\pm 14$  days).
- t. For unscheduled visits, these assessments and tests should be performed only if clinically indicated as determined by the investigator.
- u. In principle, the subject should visit the study center on the specified date. If it is not possible for subjects to visit the study center on the specified date, the date of the visit should be adjusted to the date closest to the reference date as possible.
- v. Only subjects who transferred from study RAJ1 should make study visits at Weeks 2, 4, 8, 16, 20, 28, 32, 40, and 44.

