#### **5.1.2 Increase or Reduction in Dose of the Study Drugs**

The dose increase/reduction of study drugs is allowed only when the following criteria are met. For subjects who have been receiving ASP015K at a dose of 50 mg/day in Japan, the dose will be increased to 100 mg/day after approval in Japan. Any subjects for whom the dose cannot be increased should be withdrawn from the study.

[The increase in dose from 50 mg/day to 100 mg/day]

- CONFIDENTIAL -

Japan: For subjects who have been receiving ASP015K at a dose of 50 mg/day in Japan, the dose will be increased to 100 mg/day after approval. Any subjects for whom the dose cannot be increased should be withdrawn from the study.

Korea and Taiwan: When the investigator or sub-investigator judges that there is no safety problem in the subject, the dose may be increased from 50 mg to 100 mg.

[The increase in dose from 100 mg/day to 150 mg/day]

The dose may be increased from 100 mg to 150 mg at the time point when the following 2 conditions are met:

- 1) The subject has taken ASP015K 100 mg for at least 4 weeks, and the DAS28-ESR score is 3.2 or higher (moderate disease activity or high disease activity) on the study visit days.
- 2) When the investigator or sub-investigator judges there to be no problem with safety for the subject in the assessment performed on the study visit day on which the DAS28-ESR score of 3.2 or higher was exhibited.

[The reduction in dose from 100/day mg or 150 mg/day to 50 mg/day]

Japan: After the NDA approval in Japan, dose reduction for the study drugs is not allowed.

Korea and Taiwan: After the dose increase, the dose may be reduced from 100 mg/day or 150 mg/day to 50 mg/day at the discretion of the investigator or sub-investigator.

The investigator or sub-investigator will decide whether or not to reduce the dosage on the basis of the following criterion.

- If an AE with NCI-CTCAE grade classification of Grade 2 or higher has developed.

A dose increase after a dose reduction and a dose reduction after a dose increase are allowed according to the above criteria.

If the dose of study drug has been increased or reduced, the investigator or sub-investigator should record this information in the CRF.

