### **5.1.6 Compliance Rules to be Observed by Subjects throughout the Study**

The investigator, sub-investigator, or collaborator will explain the following to the subjects during the study period.

- The subject should come to the study center on the day of each study visit without taking that day's dose of the study drug prior to the visit. The subject must also fast for at least 8 hours prior to the blood sampling at the time of the study visit. If need arises for the subject to visit the study center on an unscheduled day after taking that day's dose, for reasons such as AE, the subject should visit the study center regardless of whether and when the study drug and meal have been taken.
- If a new treatment (starting to take a new drug or use a new therapy, etc.) has been prescribed by another department or another medical institution during the study period, the subject should contact the investigator/sub-investigator before starting to use the new treatment, and follow the instructions given by the investigator/sub-investigator. If it is not possible to contact the investigator or sub-investigator in advance, the subject should contact one of them, or the collaborator, as soon as possible.
- Any subject who wishes to take a prescription medicine or over-the-counter drug unconfirmed by the investigator/sub-investigator should consult with the investigator/sub-investigator or collaborator in advance.
- Because the effects that the study drug may have upon pregnancy and the unborn child remain unclear, subjects should be certain to practice 2 or more methods of proper contraception that shall be used by male subjects throughout the study period and for 90 days after end of treatment, and by female subjects throughout the study period and for 60 days after end of treatment.

- CONFIDENTIAL -

- Female subjects must not nurse during the study period and for 60 days after the end of treatment.
- In principle, the subject will come to the study center for the study visits on the specified dates. If it is not possible to come on the specified date, the date of the visit will be adjusted to the nearest possible date.
- The subject should visit the study center without delay when instructed by the investigator or sub-investigator to do so because, for example, the laboratory testing has revealed CPK or liver function values to be in the range that requires CPK monitoring or liver function monitoring.

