- Percentage of subjects achieving DAS28-ESR score <2.6 at each analysis visit
- Percentage of subjects achieving DAS28-CRP score <=3.2 at each analysis visit
- Percentage of subjects achieving DAS28-ESR score <=3.2 at each analysis visit

Calculation DAS28-CRP/ESR response:

DAS28-CRP/ESR response is consist of following parameters, and calculated according to below description.

- o TJC (28 joints)
- o SJC (28 joints)
- CRP or ESR
- SGA

```
[When CRP is used] DAS28 = 0.56\sqrt{(TJC)} + 0.28\sqrt{(SJC)} + 0.36 \ln{(CRP + 1)} + 0.014 \times SGA + 0.96 [When ESR is used] DAS28 = 0.56\sqrt{(TJC)} + 0.28\sqrt{(SJC)} + 0.70 \ln{ESR} + 0.014 \times SGA
```

Note: CRP values measured in mg/dL will be converted to mg/L for analysis purposes as: value in mg/L = value in mg/dL \times 10; SGA is measured on 100 mm VAS. If any component is a missing value, then DAS28-CRP/ESR will be a missing value. If ESR is 0 then DAS28-ESR is missing.

- Percentage of subjects in DAS28-CRP EULAR response criterion of "Good Response" at each analysis visit
- Percentage of subjects in DAS28-ESR EULAR response criterion of "Good Response" at each analysis visit
- Percentage of subjects in DAS28-CRP EULAR response criterion of "Good Response" or "Moderate Response" at each analysis visit
- Percentage of subjects in DAS28-ESR EULAR response criterion of "Good Response" or "Moderate Response" at each analysis visit

Definition EULAR response:

DAS28 after treatment	DAS28 improvement (DAS28 before treatment - DAS28 after treatment)										
DAS28 after treatment	> 1.2	> 0.6 and $<= 1.2$	<= 0.6								
<= 3.2	Good response	Moderate response	No response								
> 3.2 and $<= 5.1$	Moderate response	Moderate response	No response								
> 5.1	Moderate response	No response	No response								

- Percentage of subjects achieving ACR/EULAR score for remission at each analysis visit If all of the following 4 parameters are fulfilled, it is defined as remission:
 - TJC (68 joints) <= 1
 - o SJC (66 joints) <= 1

 - \circ CRP <= 1 mg/dL
 - \circ SGA \leq 1 cm (on a VAS of 0-100 mm)

Note: All 4 conditions must be fulfilled to be in remission. If any component is a missing value, then ACR/EULAR score for remission will be a missing value.

- Percentage of subjects with a simplified disease activity index (SDAI) score of <= 3.3 at each analysis visit
 - SDAI score is consist of following parameters, and calculated according to below description.
 - o TJC (28 joints)
 - o SJC (28 joints)

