7.3.1 Exposure

[Analysis Set: SAF]

Duration of exposure during RAJ2 will be summarized in two ways.

- Descriptive statistics will be presented
- Exposure time for overall period will be categorized according to the following categories:
 - \circ 0 1 month
 - \circ 1 <- 3 months
 - \circ 3 <- 6 months
 - 6 <- 12 months
 - 12 <- 24 months
 - o 24 <- 36 months
 - 36 <- 48 months
 - 48 <- 60 months
 - o 60 <- 72 months
 - 72 <- 84 months
 - o 84 months <

Counts and percentages of subjects in each category will be summarized.

In addition to this, the following information on drug exposure will be presented:

- Number and percent of subject with dose increase/ dose decrease/ drug suspension/ drug interruption
- Number of experience for dose increase/ dose decrease/ drug suspension/ drug interruption per subject
- Duration from First Study Drug Taken up to First Dose Change to ASP015K 100 mg (from RAJ1) or 150 mg (from RAJ3/RAJ4)
- Maximum Dose of Study Drug (ASP015K 50 mg/ 100 mg/ 150 mg)

The following Kaplan-Meier plot of time-to-event from initial dose will be constructed.

		Event	Censor
Time to changing initial 50mg	RAJ1	Dose increase Discontinuation	Study Completion
Time to changing initial 100mg	RAJ3/4	Dose increase Dose decrease Discontinuation	Study Completion
Time to dose increasing initial 100mg	RAJ3/4	Dose increase	Study Completion Discontinuation Dose decrease
Time to dose decrease initial 100mg	RAJ3/4	Dose decrease	Study Completion Discontinuation Dose increase

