7.4.4 Influence of Dose Escalation

In order to evaluate influence of ASP015K dose escalation to 100 mg from 50 mg for subjects who shifted from RAJ1 and dose escalation to 150 mg from 100 mg for subjects who shifted from RAJ3 or RAJ4, the selected efficacy variables (ACR20-CRP and DAS28-CRP) will be analyzed based on the days of first dose increase to 100mg or 150mg until dose decrease. Following intervals will be used.

- o < -336
- o -336 < -252
- o -252 < -168
- o -168 < -84
- o -84 < 0
- 0 < 84
- o 84 < 168
- \circ 168 < 252
- o 252 < 336
- o >= 336

If multiple efficacy values are included in one interval, the last one is used.

- Graphical analysis:
 - ACR20-CRP will be plotted
 - The mean-standard deviation plot of actual values and changes from baseline of preceding study will be presented for DAS28-CRP from baseline of preceding study.

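### SAP 7.4.4 puts its dose-escalation bin edges on the RAJ3/RAJ4 visit days, so the first bin after an increase can hold a pre-escalation value or be empty

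*SAP*

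**What the plan says.** SAP 7.4.4 (Influence of Dose Escalation) covers the step from 50 to 100 mg in RAJ1 subjects and from 100 to 150 mg in RAJ3/RAJ4 subjects. ACR20-CRP and DAS28-CRP "will be analyzed based on the days of first dose increase to 100mg or 150mg until dose decrease". The cuts are at -336, -252, -168, -84, 0, 84, 168, 252 and 336 days, with open bins printed as `< -336` and `>= 336`. For repeated values the rule is: "If multiple efficacy values are included in one interval, the last one is used".

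The rest of the setting is in the protocol:

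- **Visit spacing.** Table 1, footnote v: "Only subjects who transferred from study RAJ1 should make study visits at Weeks 2, 4, 8, 16, 20, 28, 32, 40, and 44". RAJ3/RAJ4 subjects therefore attend every 12 weeks. The allowed deviation is ±7 days up to Week 48 and ±14 days from Week 60.
- **Trigger for 150 mg.** Section 5.1.2: "The dose may be increased from 100 mg to 150 mg at the time point when the following 2 conditions are met". One condition is a DAS28-ESR of at least 3.2 on a study visit day. The other is a safety judgement made "in the assessment performed on the study visit day on which the DAS28-ESR score of 3.2 or higher was exhibited". The section does not say on which day the higher dose is first taken.
- **Order of events at a visit.** Section 5.1.6: "The subject should come to the study center on the day of each study visit without taking" that day's dose.

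**The concern.** Every cut in 7.4.4 is a multiple of the RAJ3/RAJ4 visit interval, so a subject who attends on schedule is assessed close to a bin edge each time. The assessment that triggers the increase is made on the old dose, yet the bin notation would count it as after the increase if the higher dose is dated that same day.

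Section 7.4.4 is the only efficacy display aligned to the escalation date, and its purpose is to show what escalation does. If its first post-increase point mixes values taken on the old and new dose, or loses subjects to the next bin, the change looks smaller or later than it was. The SAP's Appendix 1 rules out hypothesis testing, so no error rate is involved. The issue is whether the display can be read correctly.

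**Working it through.** **1. The grid.** The RAJ3/RAJ4 reference days in SAP 7.11.5 are 7 × week + 1: 1, 85, 169, 253, 337, 421, 505 and so on. Successive differences are all 84. The 7.4.4 cuts are k × 84 for k = -4 to 4. The two grids coincide.

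**2. Bin ends.** The open bins `< -336` and `>= 336` fit only intervals closed on the left and open on the right. Day 0 then belongs to `0 < 84` and Day 84 to `84 < 168`.

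**3. Position of the next visit.** Let e1 and e2 be the deviations of the escalation visit and the next visit from schedule, and d the days from the escalation visit to the first higher dose. The next visit is on relative day 84 + e2 - e1 - d. The documents give neither d nor the distribution of e1 and e2. Below, the deviations are independent and uniform over whole days of the window; this is an assumption.

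- d = 0: `0 < 84` uses the pre-dose value when e2 - e1 ≥ 0.
- d ≥ 1: the escalation-visit value is correctly placed before Day 0, and `0 < 84` is empty when e2 - e1 ≥ d.

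| Start of higher dose | Result for `0 < 84` | On time | ±7 days | ±14 days |
|---|---|---|---|---|
| Visit day (d = 0) | pre-escalation value used | 100% | 120/225 = 53% | 435/841 = 52% |
| 1 day later | empty | 0% | 105/225 = 47% | 406/841 = 48% |
| 3 days later | empty | 0% | 78/225 = 35% | 351/841 = 42% |
| 7 days later | empty | 0% | 36/225 = 16% | 253/841 = 30% |
| 14 days later | empty | 0% | 1/225 = 0.4% | 120/841 = 14% |

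If visits move only in whole weeks, d = 0 gives 6/9 = 67% (±7) and 15/25 = 60% (±14). Delays of 1 to 7 days give 33% and 40% empty, and 14 days gives 11% and 24%.

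**4. The next bin.** With d = 0 and ±14 days, `84 < 168` holds the second post-increase visit for 48%, the first for 35%, and nothing for 17%. All its values are post-escalation, but from different visits.

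**5. Sensitivity to the bin ends.** If the intervals were instead upper-closed, a Day 0 value would count as before and on-time visits would be binned correctly. With d = 0, `0 < 84` would still be empty for 47% (±7) or 48% (±14).

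**6. RAJ1.** Before Week 48 the visits are mostly 28 days apart, so later visits fill the first bin. From Week 48 these subjects are on the same 84-day grid, although the current protocol does not tie their increase to a visit.

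**7. Other sections.** SAP 7.11.4 and 7.11.5 count windows from Day 1 of RAJ2. SAP 7.4.3 drops data after a dose change only in the initial-dose analysis. Neither settles the Day 0 value here.

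**The case against.** The strongest reply is that misclassification needs a fact the documents do not give, namely a first higher dose dated on the visit day. With a later start and on-time visits, 84-day bins on an 84-day schedule work as intended, one visit per bin. That is right, and it limits the point.

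The percentages are also scenarios. Table 1, footnote u, asks subjects to attend on the specified date or as near to it as possible, so a uniform spread is not the natural model. Unscheduled and early-termination visits can include the efficacy assessments, and 7.4.4 does not exclude them. They would lower the shares. Inclusion marks may also have been lost from the interval list when the text was extracted, although step 5 shows that a weaker form of the problem remains under upper-closed bins.

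A reader might go further and infer that the SAP leaves a Day 0 value wholly unassigned, or that about half of the first post-increase values will be pre-escalation. The documents support neither. The end bins imply a placement for Day 0, though an unhelpful one, and the start day is unknown.

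Finally, the display is descriptive, bins from Day 84 on contain only post-escalation values, and any misplacement would understate early change. That bears on severity, not on whether the text should be repaired.

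**Conclusion.** The point holds in a limited form. Following 7.4.4 as written, the first post-increase bin for RAJ3/RAJ4 subjects either uses a pre-escalation value (same-day start and next visit on Day 84 or later) or is empty (later start and a next visit late by at least the delay). Only a later start with visits that are on time, or late by less than the delay, avoids both. The figures rest on scheduled visits, left-closed bins, an assumed start day and an assumed spread of visit deviations. The geometry does not depend on the assumed spread.

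The consequence is mainly one point of a descriptive display, with change understated or shown a bin late. It is worth correcting because that point is what the display exists to show.

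**What to change.** 1. **All subjects.** Define Day 0 as the date of the first higher dose. Class any Day 0 assessment as pre-escalation. Take as reference the last assessment on or before Day 0, with no lower day limit. A limit of 42 days would leave no reference for an increase 43 to 83 days after the last visit, which is 41 of 84 possible offsets on an 84-day grid.
2. **RAJ3/RAJ4 (100 to 150 mg).** Move the edges to the midpoints between visits: Day 1-125, 126-209, 210-293, 294-377, and 378 or later. For assessments earlier than the reference, use Day -126 to -43, -210 to -127, -294 to -211, -378 to -295, and -379 or earlier. In closed windows use the value nearest Day ±84, 168, 252 or 336, and keep the last-value rule in the open ones. Reclassifying Day 0 without moving the edges is not enough: with a same-day start `0 < 84` would be empty for 100% (on time), 53% (±7) or 52% (±14). In an enumeration of the four scheduled visits on each side, all 8 × 841 × 15 = 100,920 placements (±14 days, delay 0 to 14) and all 8 × 225 × 29 = 52,200 (±7 days, delay 0 to 28) fell in their own window. The first failures come at delays of 15 and 29 days.
3. **RAJ1 (50 to 100 mg).** Keep 84-day bins and the last-value rule, but make the bins upper-closed: Day -83 to 0, 1-84, 85-168 and so on. On an on-time 84-day grid this gives one visit per closed bin at any offset. Late visits can still empty a bin.
4. **Note with the display.** The reference visit was selected on a DAS28-ESR of at least 3.2 for 100 to 150 mg increases, and also for 50 to 100 mg increases made under protocol version 1.3 (Protocol Appendix 7). SAP 6.1.1 builds DAS28-ESR and DAS28-CRP from the same joint counts and SGA, so part of the later improvement may be regression to the mean.

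The cost is one extra table of interval limits, windows that differ by preceding study, and a few sentences. No new data are needed: dose changes are recorded in the CRF, and SAP 7.3.1 already derives the time to the first dose change.

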10 APPENDICES

10.1 Appendix 1: Overview of Efficacy Endpoints

Table below summarizes the analyses of the efficacy variables, with "X" indicating that the variable will be analyzed. All analyses will be based on the FAS and presented by preceding studies, unless otherwise specified. No statistical hypothesis testing will be performed.

Overview of Efficacy Endpoints analysis

		Compone	Component for use			r Analysis		
Analysis	Type/Analysis Variable	CRP	ESR	None	RAJ1	RAJ3	RAJ4	Analysis Group
Categori	cal Variables				1	1	1	_
1.1	Percentage of subjects achieving ACR20/50/70 at each visit	X	X		X	X	X	preceding studies
1.2.1	Percentage of subjects achieving ACR20 at each visit Analysis by Treatment Sequence Set of preceding study	X			X			Treatment Sequence Set
1.2.2	Percentage of subjects achieving ACR20 at each visit Analysis by Treatment Sequence Set of preceding study	X				X		Treatment Sequence Set
1.2.3	Percentage of subjects achieving ACR20 at each visit Analysis by Treatment Sequence Set of preceding study	X					X	Treatment Sequence Set
1.3	Percentage of subjects achieving ACR20 at each visit Analysis of Efficacy in Each Dose Level	X			X	X	X	preceding studies

12-Nov-2019 Astellas Page 57 of 94

		Component for use			Study for Analysis			Analysis Croun
Analysis Ty	/pe/Analysis Variable	CRP ESR None		RAJ1	RAJ3	RAJ4	Analysis Group	
1.4.1	Percentage of subjects achieving ACR20 at each interval Influence of Dose Escalation	X			X			Subjects Who Experienced Dose Up to 100 mg
1.4.2	Percentage of subjects achieving ACR20 at each interval Influence of Dose Escalation	X				X		Subjects Who Experienced Dose Up to 150 mg
1.4.3	Percentage of subjects achieving ACR20 at each interval Influence of Dose Escalation	X					X	Subjects Who Experienced Dose Up to 150 mg

12-Nov-2019 Astellas Page 58 of 94

		Component for use			Study fo	r Analysis		
Analysis	Type/Analysis Variable	CRP	ESR	None	RAJ1	RAJ3	RAJ4	Analysis Group

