4	Percentage of subjects achieving "Good Response" or "Moderate Response" using DAS28 EULAR response criterion at each visit	X	X		X	X	X	preceding studies
5	Percentage of subjects in ACR/EULAR remission at each visit	X			X	X	X	preceding studies
6	Percentage of subjects in SDAI <= 3.3 at each visit	X			X	X	X	preceding studies

12-Nov-2019 Astellas Page 60 of 94

Anglewin Toma/Anglewin Wasinkla			ent for use		Study fo	r Analysis		A salada Gara
Analysis T	ype/Analysis Variable	CRP	ESR	None	RAJ1	RAJ3	RAJ4	Analysis Group
7	Percentage of subjects in CDAI <= 2.8 at each visit			X	X	X	X	preceding studies
8.1	Percentage of subjects achieving HAQ-DI (<=0.5) at each visit			X	X	X	X	preceding studies
8.2	Percentage of subjects achieving decrease of baseline HAQ-DI in preceding study of at least 0.22 at each visit			X	X	X	X	preceding studies
9	Percentage of subjects achieving SF-36v2 of difference >= 5 at each visit			X	X	X	X	preceding studies
Continuou	s Variables	•				•		
10.1.1	Raw value and change from baseline of preceding study in DAS28 score at each visit	X	Х		X	Х	X	preceding studies
10.1.2	Raw value and change from Week 0 in DAS28 score at each visit	X			X	X	X	preceding studies
10.2.1	Raw value and change from baseline of preceding study in DAS28 score at each visit Analysis by Treatment Sequence Set of preceding study	Х			X			Treatment Sequence Set
10.2.2	Raw value and change from baseline of preceding study in DAS28 score at each visit Analysis by Treatment Sequence Set of preceding study	Х				Х		Treatment Sequence Set

12-Nov-2019 Astellas Page 61 of 94

		Compon	ent for use		Study fo	r Analysis		
Analysis T	Sype/Analysis Variable	CRP	ESR	None	RAJ1	RAJ3	RAJ4	Analysis Group
10.2.3	Raw value and change from baseline of preceding study in DAS28 score at each visit Analysis by Treatment Sequence Set of preceding study	X					X	Treatment Sequence Set
10.3	Raw value and change from baseline of preceding study in DAS28 score at each visit Analysis of Efficacy in Each Dose Level	X			Х	X	X	preceding studies
10.4.1	Raw value and change from baseline of preceding study in DAS28 score at each interval Influence of Dose Escalation	X			Х			Subjects Who Experienced Dose Up to 100 mg
10.4.2	Raw value and change from baseline of preceding study in DAS28 score at each interval Influence of Dose Escalation	X				Х		Subjects Who Experienced Dose Up to 150 mg

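### SAP 7.4.4 lines up RAJ3/RAJ4 subjects on an increase that required a high DAS28-ESR and shows no comparator, so regression to the mean cannot be separated from a dose effect

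*SAP*

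**What the plan says.** SAP 7.4.4 sets out to evaluate what escalation does: 50 to 100 mg in subjects from RAJ1, and 100 to 150 mg in subjects from RAJ3 or RAJ4. ACR20-CRP and DAS28-CRP "will be analyzed based on the days of first dose increase to 100mg or 150mg until dose decrease". There are ten intervals, five before and five after Day 0, cut every 84 days. "If multiple efficacy values are included in one interval, the last one is used". For the plots, "The mean-standard deviation plot of actual values and changes from baseline of preceding study will be presented for DAS28-CRP". Appendix 1, items 10.4.1 to 10.4.3, matches this: "Raw value and change from baseline of preceding study in DAS28 score at each interval Influence of Dose Escalation". The analysis group for the RAJ3 and RAJ4 items is "Subjects Who Experienced Dose Up to 150 mg". No group without escalation is listed.

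Protocol 5.1.2 governs entry into this display for RAJ3/RAJ4: "The dose may be increased from 100 mg to 150 mg at the time point when the following 2 conditions are met". The first condition is "The subject has taken ASP015K 100 mg for at least 4 weeks, and the DAS28-ESR score is 3.2 or higher", judged on the visit day. The second is a safety judgement. The increase is permitted, not required.

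For RAJ1 the rule changed over time. Under ver. 1.3 (Protocol Appendix 7) the step to 100 mg also needed DAS28-ESR of 3.2 or higher, at two or more consecutive visits up to Week 12. Under the later text (Protocol 2.2.2 and 5.1.2) it is a default, a safety judgement or, in Japan after approval, mandatory. None of these has a DAS28 threshold.

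**The concern.** A score that fluctuates and is picked for being high tends to be lower next time, even if nothing changes. In RAJ3/RAJ4 every escalated subject enters at a visit picked in that way. The selection is on DAS28-ESR and the outcomes are CRP-based, but DAS28-ESR and DAS28-CRP share three of four components (both 28-joint counts and the subject's global assessment). ACR20-CRP also uses joint counts and that assessment, so the selection carries over.

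RAJ3/RAJ4 visits are 84 days apart, the same as the interval width. An interval therefore usually holds one visit, and neighbouring values do not dilute the qualifying one. At stake is whether the only analysis meant to show what 150 mg adds can say so. Neither document mentions the selection or cautions the reader about it.

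**Working it through.** **Inputs.** From the documents: threshold 3.2 (Protocol 5.1.2), 84-day intervals with the last value kept (SAP 7.4.4), 84-day visits for RAJ3/RAJ4 (Protocol Table 1). The plan states no SD, correlation or expected change for this analysis, so it has no figure to reproduce. The mean, SD and correlations below are assumptions. The true dose effect is set to zero throughout.

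**Step 1: closed form, DAS28-ESR itself.** Expected fall from a qualifying visit to a later one = (1 − ρ) × SD × φ(a) / (1 − Φ(a)), with a = (3.2 − mean) / SD.

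- Mean 3.2 gives a = 0 and φ/(1 − Φ) = 0.399/0.5 = 0.798.
- SD 1.2, ρ = 0.75: 0.25 × 1.2 × 0.798 = 0.24.
- SD 1.2, ρ = 0.6: 0.40 × 1.2 × 0.798 = 0.38.
- SD 1.2, ρ = 0.9: 0.10 × 1.2 × 0.798 = 0.10.
- Over means 2.8 to 3.8, SD 1.0 to 1.3 and ρ 0.6 to 0.9, the range is 0.05 to 0.52.

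**Step 2: simulated SAP intervals, DAS28-CRP.** Base case: mean 3.2, SD 1.2, ρ = 0.75, error correlation between the two DAS28 versions 0.9, and half of eligible visits lead to an increase. The SAP does not say which interval holds the qualifying visit, so both placements were run.

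| Qualifying visit falls in | −168 to −84 | −84 to 0 | 0 to 84 | 84 to 168 |
|---|---|---|---|---|
| −84 < 0 (higher dose starts next day) | 3.59 | 3.99 | 3.68 | 3.68 |
| 0 < 84 (higher dose starts same day) | 3.57 | 3.62 | 3.84 | 3.68 |

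- First row: false fall across Day 0 = 3.99 − 3.68 = 0.31. It is 0.14 at ρ = 0.9 and 0.45 at ρ = 0.6. With error correlation 0.7 it is 0.24. If two consecutive high visits are required, it is 0.21.
- Second row: about 53% of the values in 0 < 84 are qualifying-visit values. The false fall is 3.84 − 3.68 = 0.16 (0.07 at ρ = 0.9, 0.23 at ρ = 0.6), between two intervals that both count as after escalation. The last interval before Day 0 against 84 to 168 gives 3.68 − 3.62 = +0.06, a small rise.

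A second set of assumptions (mean 3.0, SD 1.2, ρ = 0.70/0.80/0.85, error correlation 0.85, every subject taken at the first qualifying visit) gives next-visit falls of 0.43/0.31/0.25.

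**Step 3: which reference and comparator work?** Same second set, still with no dose effect:

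- *Mean of earlier on-dose visits as reference.* Those visits were all below 3.2 by construction. The result is a false rise of 0.24 to 0.34, and 59% to 67% of subjects have no earlier value.
- *Comparator of subjects who never escalated.* This conditions on the future. If half of eligible visits escalate, never-escalators fall by 0.59 to 0.84 against 0.21 to 0.37 in escalators.
- *Comparator classified by the decision at the qualifying visit.* The two groups fall equally: 0.42 against 0.43 at ρ = 0.70.

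**The case against.** The strongest reply is that SAP 7.4.4 takes no difference from the qualifying visit. It shows raw values and change from the preceding study's baseline, over up to five earlier intervals, so a one-visit peak would be visible. It is also untested: Appendix 1 rules out hypothesis testing for the efficacy analyses.

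Part of this stands. A reader might infer that the SAP measures change from the visit that allowed the increase, but it defines no such change. The choice of baseline still does not remove the problem. It is fixed for each subject, so it drops out when a subject's intervals are compared. The earlier intervals help only partly: a subject who escalates at Week 12 has only Week 0 before it within RAJ2.

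A reader might also infer that the bias always favours the higher dose. It need not. The outer interval labels suggest intervals closed on the left, which would put a Day 0 value in 0 < 84. Same-day escalation is plausible, because subjects attend before taking that day's dose (Protocol 5.1.6) and ESR is measured at the centre (5.3.1.3). Under that reading the comparison with the last earlier interval shows +0.06.

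Nor do the documents support saying that the fall will be reported as an effect of 150 mg, or that all RAJ1 increases are affected. The EULAR cut-off of 0.6 is useful only for scale. Under the second set of assumptions 30% to 42% of subjects fall by more than that, but so do 18% to 26% of unselected stable visit pairs.

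**Conclusion.** The concern holds in limited form. For RAJ3/RAJ4, and for RAJ1 increases made under ver. 1.3, SAP 7.4.4 is an uncontrolled before-after display in subjects selected on a high DAS28-ESR. Part of any fall after the increase is expected from regression to the mean and cannot be separated from an effect of the higher dose.

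The artefact in DAS28-CRP is roughly 0.1 to 0.45 (0.07 to 0.45 across both placements of the qualifying visit), for mean about 3.0 to 3.2, SD 1.2 and ρ 0.6 to 0.9. Those inputs are not in the documents. The mechanism is well supported and the size is only indicative. The effect on ACR20-CRP was not quantified.

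**What to change.** Change SAP 7.4.4 and Appendix 1 items 1.4.2, 1.4.3, 10.4.2 and 10.4.3 as follows.

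- **(a)** Take the qualifying-visit value out of both adjoining intervals and show it as its own time point. This also settles which interval it belongs to.
- **(b)** For RAJ3/RAJ4, add the same display for visits with DAS28-ESR of 3.2 or higher after at least 4 weeks on 100 mg at which the dose was not increased. Classify by the decision at that visit, not by whether the subject ever escalated later. Cut follow-up at any later dose change, state whether a subject contributes one such visit or several, and report the result beside the escalators.
- **(c)** State that the comparison is non-randomised and descriptive.

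Do not use the mean of earlier on-dose visits as the reference, for the reason in Step 3. For RAJ1, a footnote that increases under ver. 1.3 were triggered by DAS28-ESR is enough.

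The cost is SAP wording and a few extra tables and figures from data already collected. Confounding by the investigator's choice to escalate remains. No dosing rule changes.
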